3.6 COVID-19 Modifications

If any assessments or participant contacts take place over the phone:

- The informed consent process will occur over the phone or virtual platform. The study staff will offer to email the informed consent form to the participant so that they can follow along/ have the form for their records. Documented verbal informed consent will be received before any study procedures can occur.
- All survey questions will be read to participants over the phone by a study team member. The study team member will enter the answers to these questions on REDCap on behalf of the participant.
- Training may occur over video platforms, such as Microsoft Teams- this is aligned with current strategies being used to train CHWs during COVID, delivered through the Western Cape Department of Health's People Development Centre.
- At the beginning and the end of the training we will set up a secure video call so that we may complete the pre-training and post-training role-play vignettes and adjust our scoring of these vignettes to account for this modality using an approach used in other studies using this measure and conducted during the pandemic.
- Qualitative interviews may take place in person or remotely over video platform such as Microsoft teams. Likewise, they may take place individually or in group formats to align with current guidance on social distancing.

3.7 Participant Reimbursement

3.6.1a CHW Reimbursement (Initial Pilot & Stepped-Wedge Training)

CHWs will not receive monetary compensation for the training because participation in trainings are normal and required part of their professional development for CHWs. Participation in this training as part of usual working hours will be negotiated with their NGO employers. However, attendees will be provided with meals during training and will receive reimbursement for travel when training is in-person.

The subset of CHWs participating in semi-structured qualitative interviews will receive a 150 Rand gift voucher for being consented and completing questions about their perceptions of the feasibility and acceptability of the stepped-wedge training with researchers conducted during a separate study visit with members of the research team.

3.6.1b Patient Reimbursement (Initial Pilot Only)

Patients will not receive monetary compensation for the recording of their sessions with the CHW, as these sessions are part of their normal care and evaluation of the training. Further the purpose of these recordings is for quality improvement of training rather than data collection. Patient participants will receive a 150 Rand gift voucher for being consented and completing questions about themselves and their visit with the CHW with researchers conducted during a separate study visit with members of the research team. No data will be directly collected from participants in the stepped-wedge pilot trial of the training.

3.6.1c Stakeholder Reimbursement (Stepped-Wedge Trial only)

Stakeholder participants will receive a 150 Rand gift voucher for being consented and completing questions about their perceptions of the feasibility and acceptability of the stepped-wedge training with researchers conducted during a separate study visit with members of the research team.

4. Data Analysis

4.1 Type and purpose of Data

4.1.1 Initial Pilot Training

As this is a pilot of our training, the main purpose of data collection is for us to collect sufficient information that will allow us to adapt the training for the next phase (implementation of training across six clinics). The aim of the study is not to generate effect sizes or statistical significance but rather pilot procedures including data collection procedures with patients who interact with CHWs) and gather feedback on how well these procedures worked and how they might need to be refined for the future.

This study will collect quantitative and video data from assessments with CHWs ($n = 25$) and brief assessments with their patients ($n = 75$). CHW fidelity to training will also be generated by having an independent team member listen to a subset of sessions and/or roleplays and rate the sessions on a pre-determined fidelity checklist.

Conducting roleplays both at the assessments before and after the training will also allow us to measure improvements in competencies we teach in the training (i.e., non-judgmental communication, confidentiality). If the roleplay is conducted in English, the independent rater will rate the video as they watch the video. If the session is not conducted in English, it will be translated into English and then rated along with the non-verbal communication from the video. A final competency score^{45,46} will be calculated for both pre-training and post-training roleplays for comparison.

4.1.2 Stepped Wedge Trial

The purpose of this stepped wedge trial is to examine the preliminary effectiveness and implementation of the proposed training. This study will collect the same quantitative and video data from assessments with CHWs ($n = 60$). An independent team member will rate the roleplays for both fidelity to the training using a predetermined fidelity checklist, and for stigma using the ENACT^{45,46} checklist. The fidelity rating will yield a final fidelity score, and the ENACT checklist will yield a final stigma score.

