3.5.2 Stepped Wedge Trial

3.5.2a CHW Screening & Consent

Potentially eligible CHWs—referred to us by NGO staff will be screened for eligibility. If eligible and interested in participating, they will undergo informed consent procedures. As part of this process, participants will be informed of all the potential risks and benefits to taking part in the study. Participants will be reminded that participation is voluntary, that they can decline to answer any questions they are not comfortable answering, they can leave the study at any point, and their decision to participate in the study will not impact their job. As part of signing the consent form, they will also consent to the Protection of Personal Information Act 4 of 2013.

3.5.2b CHW Baseline and Pre-Training Assessments

Baseline Assessment. Upon giving willing, informed consent, CHWs will complete a baseline assessment with study staff. The baseline assessment will consist of self-report questions around CHWs' demographic characteristics and job, personal mental health questions, questions around knowledge of HIV, TB, depression and substance use, and questions around stigma.

Pre-Treatment Assessment. Immediately before their training, participants will complete a pre-training assessment. At this visit, participants will be asked to answer the same self-report questionnaires and as they did at baseline (with the exception of demographic and job information, which will not be asked again). All CHWs will also complete a brief (~10 minutes) role-play vignette with a staff member who is minimally involved in delivering the training, which will be videotaped and later coded for stigma using the ENACT.

3.5.2c CHW Training

After the baseline assessment all groups will receive at least one dose of TAU. Based on the training time to which their cluster was randomized, CHWs will then be invited to participate in a training on mental health and substance use.

Clusters randomized to Training Time #1 will receive the training first (while the other training times continue to receive TAU), followed by Training Time #2 (while the final training time continues to receive TAU), and finally, Training Time #3.

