The training in the stepped-wedge trial will be the as the initial training, with minimal adaptations based on participant feedback (e.g., potentially an additional day, allocating more or less time to specific concepts, etc.). It will still be conducted in English, as all CHW trainings offered by the Western Cape Department of Health are required as part of the CHW certification occur in English. Roleplays will be conducted in English (training language) or isiXhosa (patients' language). Additionally, our training team consists of English, isiXhosa, and Afrikaans mother-tongue speakers; therefore, our team will be able to address questions and further explain concepts in these languages if needed.

3.5.2d CHW Post-Training Assessments

In addition to the Baseline and Pre-Treatment Assessments (which both occur before the training, and therefore, measure TAU), CHWs will also be required to complete two additional assessments after the training:

3-Month Follow-Up Assessment (3MFU): All participants will be invited to complete a follow-up assessment approximately 3-months after their training (3MFU). At this visit, participants will answer the same self-report questions they answered at the Pre-Training Assessment, answer additional questions about their perceived feasibility/acceptability of the training, and complete a roleplay for later ENACT coding.

6-Month Follow-Up Assessment (6MFU): All participants will also be invited to complete another follow-up assessment approximately 6-months after their training (6MFU). At this visit, participants will answer the same self-report questions they answered at the 3MFU and complete a roleplay for later ENACT coding. A subset of CHWs will also participate in semi-structured individual interviews in which they answer open-ended questions about their perceived feasibility/acceptability of the training.

3.5.2e Additional CHW Self-Report Measures

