CHWs will complete the same measures during the stepped-wedge trial as they did in the initial training. In addition, they will also complete an integrated measure that assesses stigmas related to HIV and TB, which has been previously validated among health workers in South Africa.^{49,50} Additionally, the personal questions around personal mental health/ substance use will be slightly expanded upon (i.e., asking about self and friends in addition to family). Although there is not an immediate post-training assessment, participants will additionally do another roleplay on their last day of training, which will be rated using the ENACT.^{45,46} Please see Initial Training Procedures (above) for more information on the roleplay.

Based on feedback from the initial training, measures used in the initial training may also be shortened or slightly reframed (e.g., only asking the feasibility and acceptability subscales of the D&I measure).

3.5.2f Stakeholder Screening and Consent

Potentially eligible NGO leaders and stakeholders will be screened for eligibility. If eligible and interested in participating, they will undergo informed consent procedures. As part of this process, participants will be informed of all the potential risks and benefits to taking part in the study. Participants will be reminded that participation is voluntary, that they can decline to answer any questions they are not comfortable answering, they can leave the study at any point, and their decision to participate in the study will not impact their job. As part of signing the consent form, they will also consent to the Protection of Personal Information Act 4 of 2013.

3.5.2g Additional Measurements

Training Feasibility. CHW attendance in the training (less than one-week) and will be assessed as one measure of training feasibility. Over 75% of training sessions attending across all CHWs will be used as a benchmark for assessing whether the training is feasible.²

CHW Fidelity. To assess the fidelity of CHW delivery of training components (e.g., using non-judgmental communication, implementing MI/PST skills), 20% of the 3MFU roleplays will be randomly selected and rated using a fidelity assessment rating form in addition to being rated on the ENACT. A fidelity score will be calculated based on the proportion of key intervention components delivered as intended across the interactions based on these ratings.

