Recordings. With the permission patients, some CHW sessions will be audio recorded for analysis. Please note that because CHWs—not patients—are the focus of these recordings, patients will not be enrolled in the study if their session is audio recorded. They will only be enrolled in the study if they choose to participate in a brief assessment about themselves and their CHW's visit. Roleplays with CHWs and either another CHW or staff member will be videorecorded. Qualitative interviews will be audio-recorded. If a roleplay, interview, or session is translated (e.g., because it is conducted in a non-English language), the translator will be a member of the study team and will leave out any potentially identifying data (e.g., names, locations). Roleplays will be recorded at the time of the training and saved in a secure location that only study-staff can access (i.e., UMD Box) and saved with the CHW's study ID. Qualitative interview recordings will also be stored in a secure location that only study-staff can access (i.e., UMD Box) and saved with the participant's study ID. CHWs will receive verbal consent from their patients before recording a normal session. If the patient does not want their session recorded, the visit will continue as usual. During training and supervision we will stress to CHWs that it is okay if none of their patients want to be recorded. If a session is recorded, the CHW will be asked to let the study team know. The study team will pick up the recording device as soon as possible and upload it to a secure database using the study computer. The audio file will then be deleted from the digital recorder. Computer audio files will be saved in a secure location that only study-staff can access (i.e., UMD Box) and saved with the CHW's study ID. Following the South African good clinical practice (GCP) guidelines and guidelines set by the American Psychological Association (APA; APA Record Keeping Guidelines, Guideline #7), recordings will be maintained until seven years after the publication of the study.). The ethics committee will review study procedures at least annually to review procedures pertaining to participant confidentiality.

Identifiable Data. Consent forms and any other documents with identifiable information will be kept in a separate, secure filing cabinet at the secure SAMRC study site.

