6.1.2 Data Entry Methods

Fidelity Analysis. Roleplays and sessions with patients and roleplays will be analysed for fidelity. If done in English, team members will review the recording in English on UMD box. If not done in English, study team members who speak isiXhosa will review the recording in isiXhosa on UMD box and complete the rating using an isiXhosa version of the measure.

Quantitative Assessments. Data entry will occur as close to real time as possible to facilitate data management and monitoring of study operations. If assessments are done on paper, they will be scanned by a research assistant as soon as possible and sent to the study's secure server. The paper assessment will then be filed away at a secure location at the MRC and the scanned assessment will be entered on REDCap.

REDCap. Demographic and measure data will utilize REDCap through UMD, a secure software toolset and workflow methodology for electronic collection and management of research and clinical trial data in real-time. SAMRC also uses REDCap for data collection. REDCap provides a web-based application with an intuitive interface for users to enter data and have real time validation rules (with automated data type and range checks) at the time of entry. REDCap data collection projects data on a thorough study-specific data dictionary defined in an iterative self-documenting process by all members of the research team with planning assistance from UMD. All information entered on REDCap will be de-identified in order to protect participants' identities.

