6.1.3 Quality Assurance

Data Completeness. To ensure the usability of self-report data, a member of the research team will review all self-report measures to ensure their completeness. Using an electronic data capture system such as REDCap is meant to reduce errors in the data entry and management process. Using REDCap, missing data can be reduced by making items required to answer before moving on to the next item and effort and error associated with data entry can be reduced because there is no manual entering of data at a later timepoint by research assistants.

Confidentiality. Data from all participants will be identified on study materials (including electronic study materials saved on a secure study drive such as Box) will be identified only by participant number and date of visit. By recording the study data in this manner, the information can be considered 'de-identified.'

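### No masking is specified for the raters who score ENACT roleplays, so expectation could inflate the secondary before-after stigma result

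*Combined protocol and SAP*

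**What the plan says.** Each CHW in the stepped-wedge trial is due to be recorded in four roleplays:

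- **Before training** (Section 3.5.2b), a roleplay "which will be videotaped and later coded for stigma using the ENACT". None is described at the baseline assessment.
- **Last day of training** (Section 3.5.2e): "participants will additionally do another roleplay on their last day of training, which will be rated using the ENACT".
- **3-month and 6-month follow-up** (Section 3.5.2d): at each visit CHWs "complete a roleplay for later ENACT coding".

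**Rating.** Section 4.1.2 states: "An independent team member will rate the roleplays for both fidelity to the training using a predetermined fidelity checklist, and for stigma" with the ENACT. Section 3.5.2g adds that "20% of the 3MFU roleplays will be randomly selected and rated using a fidelity assessment rating form in addition to being rated on the ENACT". The stepped-wedge text under Section 4.2 also confines fidelity rating to the 3-month roleplays, there without the 20% limit, and describes separate English-speaking and isiXhosa-speaking raters.

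**Labelling.** Section 6.1.3 says that participants' data on study materials, including those on a drive such as Box, "will be identified only by participant number and date of visit". Section 6.1.1 says of the recordings that they go to a secure location ("i.e., UMD Box) and saved with the CHW's study ID"), with no mention of a date. Section 5.2.2 likewise mentions only a study ID. Section 6.1.2 says, for fidelity rating, that "team members will review the recording in English on UMD box".

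**Use.** Section 4.3.1 makes ENACT a secondary measure of CHW stigma. Change in its items over the assessments is to show what training and supervision achieved and how long it lasts.

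**The concern.** The primary outcome, the Social Distance Scale, is self-reported by CHWs who know whether they have been trained. ENACT is the one stigma measure that someone else scores both before and after training, so it is the natural check on the self-report. That check is worth less if the scorer knows which recordings come after training, because the expectation of improvement runs the same way as the hypothesised effect. Each CHW has a single pre-training ENACT rating and all the others are post-training, so a timepoint-related shift in scoring looks exactly like a training effect. No planned analysis could separate the two.

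The word independent does not settle this, since the plan never defines it as masked. The safeguard in Section 3.5.2b, that the staff member in the pre-training roleplay should have little part in giving the training, concerns the roleplay partner and not the person who scores the video.

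**Working it through.** The plan gives no figure on this point, so there is nothing to reproduce. The check has two parts.

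**1. Could a rater following the plan learn the timepoint?**

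- *Masking text.* The passages on recording, storage, labelling and rating contain no statement that timepoint is hidden, that files are recoded or shuffled, or that scoring waits until all timepoints are in.
- *Dates.* If the rule in Section 6.1.3 applies to the videos, the Section 7 timeline shows what a date reveals:

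| Roleplay | Group 1 | Group 2 | Group 3 |
|---|---|---|---|
| Pre-training | month 5 | month 6 | month 7 |
| 3-month follow-up | month 9 | month 10 | month 11 |
| 6-month follow-up | month 12 | month 13 | month 14 |

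  Pre-training roleplays fall in months 5 to 7 and follow-up roleplays in months 9 to 14. The windows do not overlap, so a date from month 9 on marks a post-training video. The last-day roleplay falls around the training itself, so the month alone does not separate it from the pre-training one, but two dated files from one CHW show their order.
- *Study ID only.* If Sections 5.2.2 and 6.1.1 govern instead, the date may be absent. With four recordings per CHW, an ID alone cannot tell the files apart, and the plan does not say what does.
- *Fidelity form.* It is used only at 3 months, so a rater who is handed it knows the timepoint. Expected ENACT recordings: 60 × 4 = 240. Under Section 3.5.2g the form covers 0.20 × 60 = 12 of them (12/240 = 5%). If the text under Section 4.2 means all 3-month roleplays, it covers 60 of them (60/240 = 25%).

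**2. How much could it matter?**

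Inputs: n = 60 CHWs and a within-person correlation ρ = 0.3, both from the sample-size rationale in Section 3.3.2a, where they are planning values for the Social Distance Scale. The rater shift b, in SD units, is assumed. The true effect is set to zero, one pre-training rating is compared with one 3-month rating by a paired two-sided 5% z-test, and clinic clustering is ignored.

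SE = √(2(1 − ρ)/n) = √(2 × 0.7/60) = 0.153 SD

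Rejection probability = Φ(b/SE − 1.96) + Φ(−b/SE − 1.96)

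| Assumed shift b | n = 60, ρ = 0.3 | n = 60, ρ = 0.5 | n = 48, ρ = 0.3 |
|---|---|---|---|
| 0 | 5% | 5% | 5% |
| 0.1 SD | 10% | 12% | 9% |
| 0.2 SD | 26% | 34% | 22% |
| 0.3 SD | 50% | 64% | 42% |

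For b = 0.2: 0.2/0.1528 = 1.309, and Φ(−0.651) + Φ(−3.269) = 0.258. The last column assumes a 20% loss of CHWs, and ρ = 0.5 is also an assumption.

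**The case against.** The strongest reply is that the plan is silent on masking and that silence is not a plan to rate unmasked. A reader might infer that the videos are dated and that raters know the timepoint. The documents do not establish either. The date rule is general, and the text specific to recordings mentions only a study ID.

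The fidelity form, too, may touch as few as 12 recordings. It reveals timepoint to an ENACT scorer only if the same person receives it before scoring ENACT. No order is stated, and with raters split by language the team member in Section 4.1.2 need not be one person.

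The error rates belong to a paired test that Section 4.3.1 does not contain. One of its two ENACT analyses uses pre-training interpersonal items to predict later clinical-skills items. A uniform shift in later scores would move the intercept there and leave the slope unchanged.

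Finally, a reader might call ENACT the only observed measure of stigma, but the fidelity checklist also looks for stigmatizing conduct, though only after training and as an implementation outcome.

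All of this stands and limits the point. It does not remove it: nothing in the plan hides timepoint from the scorer, and the other ENACT analysis, improvement over the assessments, is the one exposed.

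**Conclusion.** The concern holds in this form: no masking of ENACT raters is specified, planned features could reveal timepoint, and the before-after ENACT comparison is therefore open to inflation by rater expectation. The labelling statements in Sections 5.2.2, 6.1.1 and 6.1.3 need to be reconciled.

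The size is unknown. The figures of about 10%, 26% and 50% rest on assumed shifts of 0.1, 0.2 and 0.3 SD, a test outside the plan, a correlation borrowed from another scale, and no clustering. They show sensitivity and do not estimate the trial's error rate.

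A reader might infer that the main effectiveness result is compromised. It is not, so far as rater bias goes: the Social Distance Scale has no rater, and its power calculation is untouched. This is an inexpensive improvement to a secondary outcome and should be made before scoring begins, since a rater who has learned the timepoint cannot be made to forget it.

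**What to change.** Add to Sections 4.1.2 and 4.3.1, before any ENACT scoring starts:

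1. Copy each roleplay video to a random code that carries no date, timepoint, training group or CHW ID. Staff who do not rate hold the key.
2. Within each rating language, score ENACT in a random order that mixes timepoints and clinics.
3. Lock the ENACT score before the fidelity form is assigned for any 3-month recording.
4. State in Sections 5.2.2, 6.1.1 and 6.1.3 how roleplay files are labelled, and which rule governs what raters see.

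**Cost.** The work is file renaming and a wait; no new staff, visits or recordings are needed. Scoring that mixes all timepoints cannot begin until the last 6-month roleplays are in, month 14 in the Section 7 timeline, and the fidelity scores wait with it. Section 3.3.2a selects interviewees by change in stigma without naming the measure. If ENACT was intended, its scores would not be ready when interviews start in month 13.

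**Limit.** Masking will be partial, because post-training videos may show the taught skills or a CHW may mention the training. The report should say so.
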